7.1.2 Analysis software

Analyses will be performed using Stata/SE Version 14.2 for Windows 64-bit x86-64

8. Statistical analysis

Numbers of patients screened, eligible, randomised, consented and withdrawn from the study will be reported by site. Numbers will be reported for Group A and Group B, with Group B split into 'planned' and 'rescue' subgroups. The information will be summarised as a CONSORT flow diagram. Reasons for exclusion and for withdrawal will be summarised, where reported.

Baseline demographic and clinical data will be summarised for the ITT population, for each of the two treatment groups overall and for Group A and Group B. Continuous variables will be summarized as mean (standard deviation) and median (interquartile range) whilst categorical variables will be summarized as number (percent). There will be no statistical testing for any of the summary measures whilst comparing the baseline variables between the treatment groups. The following baseline variables will be compared between the two treatment groups.

- i. Demographics
- ii. Diagnosis
- iii. Prior treatment
- iv. Physiological parameters related to oxygenation
- v. Ventilation, and
- vi. Work of breathing

For full details of included variables see Appendices.

Adherence will be reported as:

- i. Number and percentage of patients receiving the allocated treatment
- ii. Time from randomisation to initiation (separately for groups A and B)
- iii. Number and percentage of patients at correct pressure/flow rate by Hour 2
- iv. Number and percentage of patients with >50% of time at the correct pressure/flow rate in the first 6 hours
- v. Number and percentage of patients who started weaning in whom the fraction of inspired oxygen (FiO_2) was <0.40
- vi. Number and percentage of patients weaned by the correct amount
 - a. HFNC flow rate is reduced by 50%
 - b. CPAP pressure is reduced by 2 cm H_2O

Flow rate (HFNC group) and pressure (CPAP group) over time will be displayed graphically at the timepoints recorded (Hours 0, 1, 2, 3, 4, 5, 6, 12, 24, 36, 48 and 72).

Assessment of the suitability of the modified COMFORT score will be evaluated by:

- i. Number of completed measurements, reported as a percentage of all possible measurements (i.e. all time points when the patient was on HFNC or CPAP in PICU)
- ii. Number and percentage of patients with at least one measurement recorded
- iii. Mean (SD) modified COMFORT score at individual time points by tolerating allocated treatment (Yes or No) at that time point
- iv. Mean (SD) across patients of the mean within-patient modified COMFORT score for patients with a highest level of respiratory distress of moderate or severe compared with those with a highest level of none or mild

Assessment of the suitability of the PSS:PICU will be evaluated by:

- i. Number and percentage of parents returning a completed questionnaire
- ii. Number and percentage of returned questionnaires with:
 - a. All questions completed
 - b. >90% of questions completed

The number and percentage of patients experiencing treatment failures, defined as crossover or escalation to other forms of ventilation within 72 hours of randomisation, will be reported for each group. Breakdowns of the numbers of crossovers and escalation (by level of respiratory support) will be reported.

The number and percentage of patients experiencing each pre-specified adverse event (plus any other adverse events as reported) will be summarised for each treatment group. Numbers of severe adverse events and their reported relatedness to treatment will be reported in text.

The physiological effects of treatment will be presented graphically by plotting the mean \pm SD of each physiological parameter at the time points recorded (Hours 0, 1, 2, 3, 4, 5, 6, 12, 24, 36, 48 and 72).

A comparison of outcomes by treatment group will be reported for the following outcome measures:

- i. Intubation within 72 hours
- ii. Treatment failure within 72 hours (separately for crossover and escalation patients)
- iii. Length of PICU stay
- iv. Length of hospital stay
- v. Length of invasive ventilation
- vi. Length of non-invasive support
- vii. Ventilator-free days at day 28
- viii. PICU mortality
- ix. Hospital mortality

Binary outcomes will be reported as the number and percentage in each group, the risk ratio and absolute risk reduction with 95% confidence intervals. Continuous outcomes will be reported as the mean (SD) and median (IQR) in each group and the difference in means with 95% confidence interval.

Differences in treatment effect between Group A and Group B for all outcome measures will be tested as interaction tests (Mantel-Haenszel tests for binary outcomes, interaction terms in linear regression models for continuous outcomes) and presented as forest plots.

9. Reporting conventions

The following reporting conventions will be used for the SAP. These conventions will enhance the review of the study report and help to standardize presentation with common notations.

- i. Sample sizes will be presented for each treatment group as totals in the column header as “(N = xxx)”, where appropriate.
- ii. Sample sizes shown with summary statistics are the samples sizes (n) of patients with non-missing values.
- iii. All summaries for categorical variables will include all categories that were available and will not be restricted to those with at least one response.

- iv. Summaries for continuous variables that are approximately normally distributed will be reported as n, mean and standard deviation (SD).
- v. Summaries for continuous variables that are not normally distributed will be reported as n, median and quartiles.
- vi. All percentages will be rounded and reported to a single decimal place (xx.x%). A percentage of 0% will be reported as “0%”; a percentage of 100% will be reported as “100%”.
- vii. Summaries that include P-values will report the P-value to three decimal places with a leading zero (0.xxx). P-values of less than 0.0005 will be reported as “<0.001” not “0.000”.
- viii. Missing values for both numeric and string variables will be presented as dashes (“---”) or as “Not available” / “Not applicable” / “Not reported” (as appropriate) in tables or data listings.

10. Appendix – proposed tables and figures

Table 1a: Number of patients screened, eligible, consented and randomised by site

Variables	Site A	Site B	Site C	Total
Number screened, N				
Group A	XX	XX	XX	XXX
Group B:	XX	XX	XX	XXX
Planned	XX	XX	XX	XXX
Rescued	XX	XX	XX	XXX
Total	XX	XX	XX	XXX
Number of eligible patients, n (% of screened)				
Group A	XX	XX	XX	XXX
Group B:	XX	XX	XX	XXX
Planned	XX	XX	XX	XXX
Rescued	XX	XX	XX	XXX
Total	XX	XX	XX	XXX
Number of patients randomised, n (% of eligible)				
Group A	XX	XX	XX	XXX
Group B:	XX	XX	XX	XXX
Planned	XX	XX	XX	XXX
Rescued	XX	XX	XX	XXX
Total	XX	XX	XX	XXX
Consent obtained, n (% of randomised)				
Group A	XX	XX	XX	XXX
Group B:	XX	XX	XX	XXX
Planned	XX	XX	XX	XXX
Rescued	XX	XX	XX	XXX
Refused consent, n (% of randomised)				
Group A	XX	XX	XX	XXX
Group B:	XX	XX	XX	XXX
Planned	XX	XX	XX	XXX
Rescued	XX	XX	XX	XXX
Total	XX	XX	XX	XXX
Death prior to consent, n (% of randomised)				
Group A	XX	XX	XX	XXX
Group B:	XX	XX	XX	XXX
Planned	XX	XX	XX	XXX
Rescued	XX	XX	XX	XXX
Total	XX	XX	XX	XXX
Discharged prior to consent, n (% of randomised)				
Group A	XX	XX	XX	XXX
Group B:	XX	XX	XX	XXX
Planned	XX	XX	XX	XXX
Rescued	XX	XX	XX	XXX
Total	XX	XX	XX	XXX
Discontinuation/Withdrawal, n (% of consented)				
Group A	XX	XX	XX	XXX
Group B:	XX	XX	XX	XXX
Planned	XX	XX	XX	XXX
Rescued	XX	XX	XX	XXX
Total	XX	XX	XX	XXX
Number of patients analysed, n (% of randomised)				
Group A	XX	XX	XX	XXX
Group B:	XX	XX	XX	XXX

Planned	XX	XX	XX	XXX
Rescued	XX	XX	XX	XXX

Number of patients analysed but not started treatment, n (% of randomised)

Group A	XX	XX	XX	XXX
Group B:	XX	XX	XX	XXX
Planned	XX	XX	XX	XXX
Rescued	XX	XX	XX	XXX
Total	XX	XX	XX	XXX

n: Number of patients; %: Percentage of patients; N: Total number of patients

Table 1b: Number of patients consented and randomised by treatment group

Variables	HFNC	CPAP	Total
Number of patients randomised, n (% of eligible)			
Group A	XX (XX.X)	XX (XX.X)	XX (XX.X)
Group B:			
Planned	XX (XX.X)	XX (XX.X)	XX (XX.X)
Rescued	XX (XX.X)	XX (XX.X)	XX (XX.X)
Total	XX (XX.X)	XX (XX.X)	XX (XX.X)
Consent obtained, n (% of randomised)			
Group A	XX (XX.X)	XX (XX.X)	XX (XX.X)
Group B:			
Planned	XX (XX.X)	XX (XX.X)	XX (XX.X)
Rescued	XX (XX.X)	XX (XX.X)	XX (XX.X)
Total	XX (XX.X)	XX (XX.X)	XX (XX.X)
Refused consent, n (% of randomised)			
Group A	XX (XX.X)	XX (XX.X)	XX (XX.X)
Group B:			
Planned	XX (XX.X)	XX (XX.X)	XX (XX.X)
Rescued	XX (XX.X)	XX (XX.X)	XX (XX.X)
Total	XX (XX.X)	XX (XX.X)	XX (XX.X)
Death prior to consent, n (% of randomised)			
Group A	XX (XX.X)	XX (XX.X)	XX (XX.X)
Group B:			
Planned	XX (XX.X)	XX (XX.X)	XX (XX.X)
Rescued	XX (XX.X)	XX (XX.X)	XX (XX.X)
Total	XX (XX.X)	XX (XX.X)	XX (XX.X)
Discharged prior to consent, n (% of randomised)			
Group A	XX (XX.X)	XX (XX.X)	XX (XX.X)
Group B:			
Planned	XX (XX.X)	XX (XX.X)	XX (XX.X)
Rescued	XX (XX.X)	XX (XX.X)	XX (XX.X)
Total	XX (XX.X)	XX (XX.X)	XX (XX.X)
Discontinuation/Withdrawal, n (% of consented)			
Group A	XX (XX.X)	XX (XX.X)	XX (XX.X)
Group B:			
Planned	XX (XX.X)	XX (XX.X)	XX (XX.X)
Rescued	XX (XX.X)	XX (XX.X)	XX (XX.X)
Total	XX (XX.X)	XX (XX.X)	XX (XX.X)
Number of patients analysed, n (% of randomised)			
Group A	XX (XX.X)	XX (XX.X)	XX (XX.X)
Group B:			
Planned	XX (XX.X)	XX (XX.X)	XX (XX.X)
Rescued	XX (XX.X)	XX (XX.X)	XX (XX.X)
Total	XX (XX.X)	XX (XX.X)	XX (XX.X)
Number of patients analysed but not started treatment, n (% of randomised)			
Group A	XX (XX.X)	XX (XX.X)	XX (XX.X)
Group B:			
Planned	XX (XX.X)	XX (XX.X)	XX (XX.X)
Rescued	XX (XX.X)	XX (XX.X)	XX (XX.X)
Total	XX (XX.X)	XX (XX.X)	XX (XX.X)

n: Number of patients; %: Percentage of patients; N: Total number of patients

Table 2a: Baseline characteristics and clinical variables by treatment group

Variables		HFNC N = XXX	CPAP N = XXX
Demography			
Age (years)	Mean (SD)	XX.X (XX.X)	XX.X (XX.X)
	Median (IQR)	XX (XX,XX)	XX (XX,XX)
Age group, n (%)	<1 year	XX (XX.X)	XX (XX.X)
	1 to 2 years	XX (XX.X)	XX (XX.X)
	3 to 4 years	XX (XX.X)	XX (XX.X)
	5 to 9 years	XX (XX.X)	XX (XX.X)
	10 years and over	XX (XX.X)	XX (XX.X)
Gender, n (%)	Female	XX (XX.X)	XX (XX.X)
	Male	XX (XX.X)	XX (XX.X)
Weight (kg)	Mean (SD)	XX.X (XX.X)	XX.X (XX.X)
	Median (IQR)	XX (XX,XX)	XX (XX,XX)
Ethnicity, n (%)	White	XX (XX.X)	XX (XX.X)
	Mixed	XX (XX.X)	XX (XX.X)
	Asian/Asian British	XX (XX.X)	XX (XX.X)
	Black/Black British	XX (XX.X)	XX (XX.X)
	Other	XX (XX.X)	XX (XX.X)
Diagnosis			
Primary reason for PICU admission, n (%)	Bronchiolitis	XX (XX.X)	XX (XX.X)
	Asthma/Wheeze	XX (XX.X)	XX (XX.X)
	Lung disease	XX (XX.X)	XX (XX.X)
	Upper airway obstruction	XX (XX.X)	XX (XX.X)
	Neuromuscular disorder	XX (XX.X)	XX (XX.X)
	Cardiac	XX (XX.X)	XX (XX.X)
	Other	XX (XX.X)	XX (XX.X)
Prior treatment			
Length of invasive ventilation prior to extubation (days) (Group B only)	Mean (SD)	XX.X (XX.X)	XX.X (XX.X)
	Median (IQR)	XX (XX,XX)	XX (XX,XX)
Modified COMFORT score at baseline	Mean (SD)	XX.X (XX.X)	XX.X (XX.X)
	Median (IQR)	XX (XX,XX)	XX (XX,XX)
Physiology at baseline			
Respiratory rate (breaths min ⁻¹)	Mean (SD)	XX.X (XX.X)	XX.X (XX.X)
	Median (IQR)	XX (XX,XX)	XX (XX,XX)
Heart rate (beats min ⁻¹)	Mean (SD)	XX.X (XX.X)	XX.X (XX.X)
	Median (IQR)	XX (XX,XX)	XX (XX,XX)
SpO ₂ (%)	Mean (SD)	XX.X (XX.X)	XX.X (XX.X)
	Median (IQR)	XX (XX,XX)	XX (XX,XX)
PaO ₂ (kPa)	Mean (SD)	X.X (X.X)	X.X (X.X)

FiO ₂	Median (IQR)	X.X (X.X,X.X)	X.X (X.X,X.X)
	Mean (SD) Median (IQR)	X.XX (X.XX) X.XX (X.XX,X.XX)	X.XX (X.XX) X.XX (X.XX,X.XX)
pH	Mean (SD) Median (IQR)	X.XX (X.XX) X.XX (X.XX,X.XX)	X.XX (X.XX) X.XX (X.XX,X.XX)
	pCO ₂ (kPa)		
	Mean (SD) Median (IQR)	X.X (X.X) X.X (X.X,X.X)	X.X (X.X) X.X (X.X,X.X)
	Work of breathing		
Respiratory distress, n (%)			
	None	XX (XX.X)	XX (XX.X)
	Mild	XX (XX.X)	XX (XX.X)
	Moderate	XX (XX.X)	XX (XX.X)
	Severe	XX (XX.X)	XX (XX.X)

n: Number of patients; %: Percentage of patients; N: Total number of patients;
SD: Standard deviation; IQR: Inter-quartile range

Table 2b: Baseline characteristics and clinical variables by treatment group – Group A

Variables		HFNC N = XXX	CPAP N = XXX
Demography			
Age (years)	Mean (SD)	XX.X (XX.X)	XX.X (XX.X)
	Median (IQR)	XX (XX,XX)	XX (XX,XX)
Age group, n (%)	<1 year	XX (XX.X)	XX (XX.X)
	1 to 2 years	XX (XX.X)	XX (XX.X)
	3 to 4 years	XX (XX.X)	XX (XX.X)
	5 to 9 years	XX (XX.X)	XX (XX.X)
	10 years and over	XX (XX.X)	XX (XX.X)
Gender, n (%)	Female	XX (XX.X)	XX (XX.X)
	Male	XX (XX.X)	XX (XX.X)
Weight (kg)	Mean (SD)	XX.X (XX.X)	XX.X (XX.X)
	Median (IQR)	XX (XX,XX)	XX (XX,XX)
Ethnicity, n (%)	White	XX (XX.X)	XX (XX.X)
	Mixed	XX (XX.X)	XX (XX.X)
	Asian/Asian British	XX (XX.X)	XX (XX.X)
	Black/Black British	XX (XX.X)	XX (XX.X)
	Other	XX (XX.X)	XX (XX.X)
Diagnosis			
Primary reason for PICU admission, n (%)	Bronchiolitis	XX (XX.X)	XX (XX.X)
	Asthma/Wheeze	XX (XX.X)	XX (XX.X)
	Lung disease	XX (XX.X)	XX (XX.X)
	Upper airway obstruction	XX (XX.X)	XX (XX.X)
	Neuromuscular disorder	XX (XX.X)	XX (XX.X)
	Cardiac	XX (XX.X)	XX (XX.X)
	Other	XX (XX.X)	XX (XX.X)
Prior treatment			
Modified COMFORT score at baseline	Mean (SD)	XX.X (XX.X)	XX.X (XX.X)
	Median (IQR)	XX (XX,XX)	XX (XX,XX)
Physiology at baseline			
Respiratory rate (breaths min ⁻¹)	Mean (SD)	XX.X (XX.X)	XX.X (XX.X)
	Median (IQR)	XX (XX,XX)	XX (XX,XX)
Heart rate (beats min ⁻¹)	Mean (SD)	XX.X (XX.X)	XX.X (XX.X)
	Median (IQR)	XX (XX,XX)	XX (XX,XX)
SpO ₂ (%)	Mean (SD)	XX.X (XX.X)	XX.X (XX.X)
	Median (IQR)	XX (XX,XX)	XX (XX,XX)
PaO ₂ (kPa)	Mean (SD)	X.X (X.X)	X.X (X.X)
	Median (IQR)	X.X (X.X,X.X)	X.X (X.X,X.X)
FiO ₂	Mean (SD)	X.XX (X.XX)	X.XX (X.XX)
	Median (IQR)	X.XX	X.XX

pH		(X.XX,X.XX)	(X.XX,X.XX)
	Mean (SD)	X.XX (X.XX)	X.XX (X.XX)
pCO ₂ (kPa)	Median (IQR)	X.XX (X.XX,X.XX)	X.XX (X.XX,X.XX)
	Mean (SD)	X.X (X.X)	X.X (X.X)
Work of breathing	Median (IQR)	X.X (X.X,X.X)	X.X (X.X,X.X)
	Respiratory distress, n (%)		
	None	XX (XX.X)	XX (XX.X)
	Mild	XX (XX.X)	XX (XX.X)
	Moderate	XX (XX.X)	XX (XX.X)
	Severe	XX (XX.X)	XX (XX.X)

n: Number of patients; %: Percentage of patients; N: Total number of patients;
SD: Standard deviation; IQR: Inter-quartile range

Table 2c: Baseline characteristics and clinical variables by treatment group – Group B

Variables	Planned		Rescued	
	HFNC	CPAP	HFNC	CPAP
	N = XXX	N = XXX	N = XXX	N = XXX
Demography				
Age (years)				
Mean (SD)	XX.X (XX.X)	XX.X (XX.X)	XX.X (XX.X)	XX.X (XX.X)
Median (IQR)	XX (XX,XX)	XX (XX,XX)	XX (XX,XX)	XX (XX,XX)
Age group, n (%)				
<1 year	XX (XX.X)	XX (XX.X)	XX (XX.X)	XX (XX.X)
1 to 2 years	XX (XX.X)	XX (XX.X)	XX (XX.X)	XX (XX.X)
3 to 4 years	XX (XX.X)	XX (XX.X)	XX (XX.X)	XX (XX.X)
5 to 9 years	XX (XX.X)	XX (XX.X)	XX (XX.X)	XX (XX.X)
10 years and over	XX (XX.X)	XX (XX.X)	XX (XX.X)	XX (XX.X)
Gender, n (%)				
Female	XX (XX.X)	XX (XX.X)	XX (XX.X)	XX (XX.X)
Male	XX (XX.X)	XX (XX.X)	XX (XX.X)	XX (XX.X)
Weight (kg)				
Mean (SD)	XX.X (XX.X)	XX.X (XX.X)	XX.X (XX.X)	XX.X (XX.X)
Median (IQR)	XX (XX,XX)	XX (XX,XX)	XX (XX,XX)	XX (XX,XX)
Ethnicity, n (%)				
White	XX (XX.X)	XX (XX.X)	XX (XX.X)	XX (XX.X)
Mixed	XX (XX.X)	XX (XX.X)	XX (XX.X)	XX (XX.X)
Asian/Asian British	XX (XX.X)	XX (XX.X)	XX (XX.X)	XX (XX.X)
Black/Black British	XX (XX.X)	XX (XX.X)	XX (XX.X)	XX (XX.X)
Other	XX (XX.X)	XX (XX.X)	XX (XX.X)	XX (XX.X)
Diagnosis				
Primary reason for PICU admission, n (%)				
Bronchiolitis	XX (XX.X)	XX (XX.X)	XX (XX.X)	XX (XX.X)
Asthma/Wheeze	XX (XX.X)	XX (XX.X)	XX (XX.X)	XX (XX.X)
Lung disease	XX (XX.X)	XX (XX.X)	XX (XX.X)	XX (XX.X)
Upper airway obstruction	XX (XX.X)	XX (XX.X)	XX (XX.X)	XX (XX.X)
Neuromuscular disorder	XX (XX.X)	XX (XX.X)	XX (XX.X)	XX (XX.X)
Cardiac	XX (XX.X)	XX (XX.X)	XX (XX.X)	XX (XX.X)
Other	XX (XX.X)	XX (XX.X)	XX (XX.X)	XX (XX.X)
Prior treatment				
Length of invasive ventilation prior to extubation (days)				
Mean (SD)	XX.X (XX.X)	XX.X (XX.X)	XX.X (XX.X)	XX.X (XX.X)
Median (IQR)	XX (XX,XX)	XX (XX,XX)	XX (XX,XX)	XX (XX,XX)
Modified COMFORT score at baseline				
Mean (SD)	XX.X (XX.X)	XX.X (XX.X)	XX.X (XX.X)	XX.X (XX.X)
Median (IQR)	XX (XX,XX)	XX (XX,XX)	XX (XX,XX)	XX (XX,XX)
Physiology at baseline				
Respiratory rate (breaths min ⁻¹)				
Mean (SD)	XX.X (XX.X)	XX.X (XX.X)	XX.X (XX.X)	XX.X (XX.X)
Median (IQR)	XX (XX,XX)	XX (XX,XX)	XX (XX,XX)	XX (XX,XX)
Heart rate (beats min ⁻¹)				
Mean (SD)	XX.X (XX.X)	XX.X (XX.X)	XX.X (XX.X)	XX.X (XX.X)
Median (IQR)	XX (XX,XX)	XX (XX,XX)	XX (XX,XX)	XX (XX,XX)
SpO ₂ (%)				

	Mean (SD)	XX.X (XX.X)	XX.X (XX.X)	XX.X (XX.X)	XX.X (XX.X)
	Median (IQR)	XX (XX,XX)	XX (XX,XX)	XX (XX,XX)	XX (XX,XX)
PaO ₂ (kPa)					
	Mean (SD)	X.X (X.X)	X.X (X.X)	X.X (X.X)	X.X (X.X)
	Median (IQR)	X.X (X.X,X.X)	X.X (X.X,X.X)	X.X (X.X,X.X)	X.X (X.X,X.X)
FiO ₂					
	Mean (SD)	X.XX (X.XX)	X.XX (X.XX)	X.XX (X.XX)	X.XX (X.XX)
	Median (IQR)	X.XX (X.XX,X.XX)	X.XX (X.XX,X.XX)	X.XX (X.XX,X.XX)	X.XX (X.XX,X.XX)
pH					
	Mean (SD)	X.XX (X.XX)	X.XX (X.XX)	X.XX (X.XX)	X.XX (X.XX)
	Median (IQR)	X.XX (X.XX,X.XX)	X.XX (X.XX,X.XX)	X.XX (X.XX,X.XX)	X.XX (X.XX,X.XX)
pCO ₂ (kPa)					
	Mean (SD)	X.X (X.X)	X.X (X.X)	X.X (X.X)	X.X (X.X)
	Median (IQR)	X.X (X.X,X.X)	X.X (X.X,X.X)	X.X (X.X,X.X)	X.X (X.X,X.X)
Work of breathing					
Respiratory distress, n (%)					
	None	XX (XX.X)	XX (XX.X)	XX (XX.X)	XX (XX.X)
	Mild	XX (XX.X)	XX (XX.X)	XX (XX.X)	XX (XX.X)
	Moderate	XX (XX.X)	XX (XX.X)	XX (XX.X)	XX (XX.X)
	Severe	XX (XX.X)	XX (XX.X)	XX (XX.X)	XX (XX.X)

n: Number of patients; %: Percentage of patients; N: Total number of patients;
SD: Standard deviation; IQR: Inter-quartile range

Table 3: Adherence by treatment groups

Variables		HFNC	CPAP
		N = XXX	N = XXX
Initiation:			
Randomised treatment started, n/N (%)			
Group A		XX/XX (XX.X)	XX/XX (XX.X)
Group B		XX/XX (XX.X)	XX/XX (XX.X)
Total		XX/XX (XX.X)	XX/XX (XX.X)
Time from randomisation to initiation (hours)			
Mean (SD)			
Group A		XX.X (XX.X)	XX.X (XX.X)
Group B:			
Planned		XX.X (XX.X)	XX.X (XX.X)
Rescued		XX.X (XX.X)	XX.X (XX.X)
Total		XX.X (XX.X)	XX.X (XX.X)
Median (IQR)			
Group A		XX (XX,XX)	XX (XX,XX)
Group B:			
Planned		XX (XX,XX)	XX (XX,XX)
Rescued		XX (XX,XX)	XX (XX,XX)
Total		XX (XX,XX)	XX (XX,XX)
Maintenance:			
At correct pressure/flow rate by Hour 2, n/N (%)			
Group A		XX/XX (XX.X)	XX/XX (XX.X)
Group B		XX/XX (XX.X)	XX/XX (XX.X)
Total		XX/XX (XX.X)	XX/XX (XX.X)
Treated >50% of time at correct pressure/flow rate in first 6 hours, n/N (%)			
Group A		XX/XX (XX.X)	XX/XX (XX.X)
Group B		XX/XX (XX.X)	XX/XX (XX.X)
Total		XX/XX (XX.X)	XX/XX (XX.X)
Weaning:			
Proportion started weaning in whom FiO ₂ was <0.40, n/N (%)			
Group A		XX/XX (XX.X)	XX/XX (XX.X)
Group B		XX/XX (XX.X)	XX/XX (XX.X)
Total		XX/XX (XX.X)	XX/XX (XX.X)
Proportion weaned by correct amount, n/N (%)			
Group A		XX/XX (XX.X)	XX/XX (XX.X)
Group B		XX/XX (XX.X)	XX/XX (XX.X)
Total		XX/XX (XX.X)	XX/XX (XX.X)

n: Number of patients; %: Percentage of patients; N: Total number of patients;
SD: Standard deviation; IQR: Inter-quartile range

Table 4: Modified COMFORT score and PSS:PICU by treatment group

Variables	HFNC	CPAP
	N = XXX	N = XXX
Modified COMFORT score:		
Modified COMFORT score completed, n/N (% of all eligible time points)		
Group A	XX (XX.X)	XX (XX.X)
Group B	XX (XX.X)	XX (XX.X)
Total	XX (XX.X)	XX (XX.X)
Patients with at least one modified COMFORT score completed, n/N (%)		
Group A	XX (XX.X)	XX (XX.X)
Group B	XX (XX.X)	XX (XX.X)
Total	XX (XX.X)	XX (XX.X)
Modified COMFORT score (Hour 1-6) by tolerating randomised treatment at individual time points, mean (SD) [N]		
Group A		
Yes	XX.X (XX.X) [XX]	XX.X (XX.X) [XX]
No	XX.X (XX.X) [XX]	XX.X (XX.X) [XX]
Group B		
Yes	XX.X (XX.X) [XX]	XX.X (XX.X) [XX]
No	XX.X (XX.X) [XX]	XX.X (XX.X) [XX]
Mean modified COMFORT score (Hour 1-6) by patient's highest level of respiratory distress, mean (SD) [N]		
Group A		
None/Mild	XX.X (XX.X) [XX]	XX.X (XX.X) [XX]
Moderate/Severe	XX.X (XX.X) [XX]	XX.X (XX.X) [XX]
Group B		
None/Mild	XX.X (XX.X) [XX]	XX.X (XX.X) [XX]
Moderate/Severe	XX.X (XX.X) [XX]	XX.X (XX.X) [XX]
Use of sedative agents, n (%):		
Group A	XX (XX.X)	XX (XX.X)
Group B	XX (XX.X)	XX (XX.X)
Total	XX (XX.X)	XX (XX.X)
PSS:PICU:		
PSS:PICU questionnaire returned, n/N (%)		
Group A	XX (XX.X)	XX (XX.X)
Group B	XX (XX.X)	XX (XX.X)
Total	XX (XX.X)	XX (XX.X)
PSS:PICU questionnaire 100% complete, n/N (%)		
Group A	XX (XX.X)	XX (XX.X)
Group B	XX (XX.X)	XX (XX.X)
Total	XX (XX.X)	XX (XX.X)
PSS:PICU questionnaire >90% complete, n/N (%)		
Group A	XX (XX.X)	XX (XX.X)

	Group B	XX (XX.X)	XX (XX.X)
	Total	XX (XX.X)	XX (XX.X)
PSS:PICU	Group A:		
	Mean (SD)	XX.X (XX.X)	XX.X (XX.X)
	Median (IQR)	XX (XX,XX)	XX (XX,XX)
	Group B:		
	Mean (SD)	XX.X (XX.X)	XX.X (XX.X)
	Median (IQR)	XX (XX,XX)	XX (XX,XX)

n: Number of patients; %: Percentage of patients; N: Total number of patients;
SD: Standard deviation

Table 5: Treatment failure by treatment group

Variables	HFNC	CPAP
	N = XXX	N = XXX
Treatment failure:		
Crossover or escalation to other forms of ventilation within 72 hours of randomisation, n/N (%)		
Group A	XX/XX (XX.X)	XX/XX (XX.X)
Group B	XX/XX (XX.X)	XX/XX (XX.X)
Total	XX/XX (XX.X)	XX/XX (XX.X)
Crossover:		
Crossover from HFNC to CPAP or CPAP to HFNC, n/N (%)		
Group A	XX/XX (XX.X)	XX/XX (XX.X)
Group B	XX/XX (XX.X)	XX/XX (XX.X)
Total	XX/XX (XX.X)	XX/XX (XX.X)
Treatment escalation:		
Intubation and ventilation, n/N (%)		
Group A	XX/XX (XX.X)	XX/XX (XX.X)
Group B	XX/XX (XX.X)	XX/XX (XX.X)
Total	XX/XX (XX.X)	XX/XX (XX.X)
Non-invasive CPAP/PS, n/N (%)		
Group A	XX/XX (XX.X)	XX/XX (XX.X)
Group B	XX/XX (XX.X)	XX/XX (XX.X)
Total	XX/XX (XX.X)	XX/XX (XX.X)
Non-invasive BiPAP, n/N (%)		
Group A	XX/XX (XX.X)	XX/XX (XX.X)
Group B	XX/XX (XX.X)	XX/XX (XX.X)
Total	XX/XX (XX.X)	XX/XX (XX.X)
Other, n/N (%)		
Group A	XX/XX (XX.X)	XX/XX (XX.X)
Group B	XX/XX (XX.X)	XX/XX (XX.X)
Total	XX/XX (XX.X)	XX/XX (XX.X)

n: Number of patients; %: Percentage of patients; N: Total number of patients

Table 6: Adverse events by treatment group

Variables		HFNC	CPAP
		N = XXX	N = XXX
Safety - Adverse events			
Pneumothorax, n (%)			
	Group A	XX (XX.X)	XX (XX.X)
	Group B	XX (XX.X)	XX (XX.X)
	Total	XX (XX.X)	XX (XX.X)
Pneumomediastinum, n (%)			
	Group A	XX (XX.X)	XX (XX.X)
	Group B	XX (XX.X)	XX (XX.X)
	Total	XX (XX.X)	XX (XX.X)
Subcutaneous emphysema, n (%)			
	Group A	XX (XX.X)	XX (XX.X)
	Group B	XX (XX.X)	XX (XX.X)
	Total	XX (XX.X)	XX (XX.X)
Abdominal distension, n (%)			
	Group A	XX (XX.X)	XX (XX.X)
	Group B	XX (XX.X)	XX (XX.X)
	Total	XX (XX.X)	XX (XX.X)
Nasal trauma, n (%)			
	Group A	XX (XX.X)	XX (XX.X)
	Group B	XX (XX.X)	XX (XX.X)
	Total	XX (XX.X)	XX (XX.X)
Facial trauma, n (%)			
	Group A	XX (XX.X)	XX (XX.X)
	Group B	XX (XX.X)	XX (XX.X)
	Total	XX (XX.X)	XX (XX.X)
Facial thermal injury, n (%)			
	Group A	XX (XX.X)	XX (XX.X)
	Group B	XX (XX.X)	XX (XX.X)
	Total	XX (XX.X)	XX (XX.X)
Respiratory/Cardiac arrest, n (%)			
	Group A	XX (XX.X)	XX (XX.X)
	Group B	XX (XX.X)	XX (XX.X)
	Total	XX (XX.X)	XX (XX.X)
Aspiration, n (%)			
	Group A	XX (XX.X)	XX (XX.X)
	Group B	XX (XX.X)	XX (XX.X)
	Total	XX (XX.X)	XX (XX.X)
Other ^a , n (%)			
	Group A	XX (XX.X)	XX (XX.X)
	Group B	XX (XX.X)	XX (XX.X)
	Total	XX (XX.X)	XX (XX.X)

n: Number of patients; %: Percentage of patients; N: Total number of patients

^a Other reported adverse events were...

Table 7: Comparison of outcomes by treatment group

Outcome	HFNC	CPAP	Effect estimates (95% CI)	P value
	N = XXX	N = XXX		
Intubation within 72h				
n (%)	XX (XX.X)	XX (XX.X)	Risk ratio: X.XX (X.XX, X.XX) Absolute risk reduction: XX.X (XX.X, XX.X)	0.XXX
Treatment failure within 72h				
n (%)	XX (XX.X)	XX (XX.X)	Risk ratio: X.XX (X.XX, X.XX) Absolute risk reduction: XX.X (XX.X, XX.X)	0.XXX
Length of PICU stay from randomisation (days):				
Mean (SD)	X.X (X.X)	X.X (X.X)	Mean difference: X.X (X.X,X.X)	0.XXX
Median (IQR)	X.X (X.X,X.X)	X.X (X.X,X.X)		
Length of hospital stay (days)				
Mean (SD)	X.X (X.X)	X.X (X.X)	Mean difference: X.X (X.X,X.X)	0.XXX
Median (IQR)	XX (XX,XX)	XX (XX,XX)		
Length of invasive ventilation (days)				
Mean (SD)	X.X (X.X)	X.X (X.X)	Mean difference: X.X (X.X,X.X)	0.XXX
Median (IQR)	XX (XX,XX)	XX (XX,XX)		
Length of non-invasive respiratory support (days)				
Mean (SD)	X.X (X.X)	X.X (X.X)	Mean difference: X.X (X.X,X.X)	0.XXX
Median (IQR)	XX (XX,XX)	XX (XX,XX)		
Ventilator-free days at day 28				
Mean (SD)	X.X (X.X)	X.X (X.X)	Mean difference: X.X (X.X,X.X)	0.XXX
PICU mortality				
n (%)	XX (XX.X)	XX (XX.X)	Risk ratio: X.XX (X.XX, X.XX) Absolute risk reduction: XX.X (XX.X, XX.X)	0.XXX
Hospital mortality				
n (%)	XX (XX.X)	XX (XX.X)	Risk ratio: X.XX (X.XX, X.XX) Absolute risk reduction: XX.X (XX.X, XX.X)	0.XXX

n: Number of patients; %: Percentage of patients; N: Total number of patients;
SD: Standard deviation; IQR: Inter-quartile range

Figure 1: Study flow diagram

CONSORT flow diagram

Figure 2: Flow rate/pressure over time

Mean (SD) at Hours 0, 1, 2, 3, 4, 5, 6, 12, 24, 36, 48 and 72. Panels for:

- Flow rate (<10 kg vrs ≥10 kg - l kg⁻¹ min⁻¹) – HFNC group
- Pressure (cmH₂O) – CPAP group

Figure 3: Physiology/comfort/respiratory distress over time

Mean (SD), unless indicated, by treatment group at Hours 0, 1, 2, 3, 4, 5, 6, 12, 24, 36, 48 and 72. Panels (Group A and Group B) for:

- Respiratory rate (breaths min⁻¹)
- Heart rate (beats min⁻¹)
- SpO₂ (%)
- PaO₂ (kPa)
- FiO₂
- pH
- pCO₂ (kPa)
- Modified COMFORT score
- Percentage with Moderate/Severe respiratory distress

Numbers at the foot of each figure will indicate the number of patients with measurements at each timepoint.

Figure 4: Forest plot of outcomes

All outcomes from Table 7 reported for Group A, Group B and overall with test of interaction. Panels for (A) binary outcomes (risk ratio); and (B) continuous outcomes (difference in means).

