2.1 Primary objectives

The primary objective of this study is to determine the feasibility of an RCT of HFNC versus CPAP in critically ill children. This objective was measured based on the following endpoints:

- i. Assess the number of eligible patients in Group A (step-up) and Group B (step-down)
- ii. Assess the acceptability of using a mixed model of consent (prospective and deferred)
- iii. Assess the feasibility of randomising at least 50% of eligible patients
- iv. Test the practical aspects of implementing the study protocol in terms of initiation, maintenance and weaning of the study intervention
- v. Assess whether a modified COMFORT score (COMFORT score minus the respiratory component) can be used to measure patient tolerance to CPAP/HFNC
- vi. Assess the feasibility of using the Parental Stressor Scale: PICU (PSS:PPICU) to measure parental stress 24 hours after the initiation of CPAP/HFNC

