4.1 Inclusion criteria of patients

In order to minimise variation in practice between and within centres predefined, objective criteria were specified to provide clear directions to clinicians to guide the decision on when to start NRS. Eligible patients fell into one of two groups:

Group A (Step-up)

- i. Age >36 weeks corrected gestational age and <16 years, and
- ii. Deemed to require non-invasive respiratory support by the treating clinician for an acute illness, and
- iii. Satisfies one or more of the following criteria:
 - a. Hypoxia (oxygen saturation <92% in $FiO_2 >0.40$, or equivalent). FiO_2 of 0.40 roughly equates to standard unhumidified nasal cannula oxygen delivered at 6 L/min or oxygen delivered via facemask without a rebreather bag at 6-10 L/min
 - b. Acute respiratory acidosis (pH <7.3 with a concomitant $pCO_2 >6.5$ kPa)
 - c. Moderate respiratory distress (use of accessory muscles, subcostal and intercostal recession, tachypnoea for age, grunting)

Group B (Step-down)

- i. Age >36 weeks corrected for gestation and <16 years, and
- ii. Deemed to require non-invasive respiratory support by the treating clinician after extubation, following a spell of invasive ventilation:
 - a. Either immediately after extubation as a 'planned' procedure, irrespective of clinical condition ('planned') or
 - b. Prompted by deterioration in clinical condition within 72 hours after extubation ('rescue'). Clinical parameters to assess the need for NRS in this situation will be similar to point 3 in Group A

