5.1 Primary outcomes

The primary outcomes of this study measure the respective primary objectives stated in section 2.1.

- i. Estimate the number of eligible patients in Group A (step-up) and Group B (step-down)
- ii. Examine the acceptability of using a mixed model of consent (prospective and deferred), i.e. estimate the number of prospective and deferred consent among the treatment groups
- iii. Assess the feasibility of randomising at least 50% of eligible patients, i.e. examine if 50% of the eligible patients were randomised into the trial
- iv. Test the practical aspects of implementing the study protocol in terms of initiation, maintenance and weaning of the study intervention, i.e. estimate:
 - a. Initiation
 - Proportion receiving allocated treatment
 - Time from randomisation to initiation
 - b. Maintenance (excluding patients who did not continue treatment for the full six hours)
 - Proportion at correct pressure/flow rate by Hour 2
 - Proportion with >50% of time at correct pressure/flow rate in first 6 hours
 - c. Weaning
 - Proportion started weaning when should (by next time point)
 - Proportion weaned by prescribed flow rate (HFNC) or pressure (CPAP) according to protocol
- v. Assess whether a modified COMFORT score (COMFORT score minus the respiratory component) can be used to measure patient tolerance to CPAP/HFNC, i.e. estimate:
 - a. Number of completed COMFORT scores
 - b. Number of lower COMFORT scores when not tolerating (within/between patients)

- vi. Assess the feasibility of using the Parental Stressor Scale: PICU (PSS:PPICU) to measure parental stress 24 hours after the initiation of CPAP/HFNC, i.e. estimate:
 - b. Number of questionnaires returned
 - c. Number/quality of questionnaires completed

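### The weaning-start measure in SAP Section 8 (Adherence v) and Table 3 has no time window and no clear denominator, so it does not report the Section 5.1 outcome

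*SAP*

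**What the plan says.** Weaning belongs to the fourth primary objective in SAP Section 2.1: "Test the practical aspects of implementing the study protocol in terms of initiation, maintenance and weaning of the study intervention".

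Section 5.1 iv.c turns this into two weaning measures. The first is "Proportion started weaning when should (by next time point". The second concerns the size of the weaning step.

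Section 8, Adherence v, gives the analysis of the first measure as "Number and percentage of patients who started weaning in whom the fraction of inspired oxygen" (FiO2) was below 0.40. Table 3 in the Section 10 appendix has the matching row: "Proportion started weaning in whom FiO ₂ was <0.40, n/N", by Group A, Group B and total. Adherence vi and the last row of Table 3 cover the size of the step.

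Section 8 also gives the schedule on which flow and pressure are displayed: "at the timepoints recorded (Hours 0, 1, 2, 3, 4, 5, 6, 12, 24, 36, 48 and 72".

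**The concern.** The Section 5.1 outcome asks whether weaning began on time once it was due. The Section 8 and Table 3 measure asks only whether two things are true of the same patient: weaning started, and FiO2 was below 0.40. The window has gone. The phrase that links the two conditions also leaves open which one defines the denominator.

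What is at stake is one part of the answer to whether the study protocol can be implemented. An analyst who follows Section 8 and fills in Table 3 would publish a percentage that looks like adherence to weaning but cannot distinguish prompt from late weaning. An analyst who notices the gap would have to choose the numerator, denominator and window after the data are available. The SAP's introduction says it is agreed in advance to avoid exactly that kind of decision.

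**Working it through.** The SAP states no figure for this measure, so there is nothing to reproduce. The check sets the texts side by side and then shows what the difference does to a proportion.

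**Step 1. Compare the three places.**

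| Place | Condition | Time window | Denominator |
|---|---|---|---|
| Section 5.1 iv.c | Started weaning when due | By the next time point | Implied: patients due to wean |
| Section 8, Adherence v | Started weaning; FiO2 <0.40 | None | Not stated |
| Table 3, weaning row | Started weaning; FiO2 <0.40 | None | N shown, not defined |

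**Step 2. Look for the timing elsewhere.** Adherence vi concerns step size only. Figure 2 plots group means of flow or pressure and does not show when an individual was due to wean or began. No other listed item, table or figure reports when weaning began relative to when it was due.

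**Step 3. Compare with the neighbouring items.** Adherence iii keeps the Hour 2 limit from Section 5.1, and Adherence iv keeps the first-6-hours limit. The weaning-start item is the one that loses its time limit between the two sections.

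**Step 4. Write out the readings.** For illustration, take FiO2 <0.40 as the trigger, as Adherence v suggests. In one arm let

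- a = patients who reach the trigger and start weaning by the next time point
- b = patients who reach it and start later
- c = patients who reach it and never start
- d = patients who start weaning with FiO2 at or above 0.40

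Then:

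- Section 5.1 outcome: a / (a + b + c)
- Section 8 v, N = patients with FiO2 <0.40: (a + b) / (a + b + c)
- Section 8 v, N = patients who started weaning: (a + b) / (a + b + d)

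Both Section 8 readings contain a and b only as the sum a + b, so neither changes when patients move from on time to late. The first reading exceeds the Section 5.1 outcome by b / (a + b + c). The second does not contain c at all.

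**Step 5. Put in assumed counts.** These are not from the SAP: a = 30, b = 15, c = 5, d = 3.

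- Section 5.1 outcome: 30 / 50 = 60.0%
- First Section 8 reading: 45 / 50 = 90.0%
- Second Section 8 reading: 45 / 48 = 93.8%

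With a + b, c and d held fixed, the Section 5.1 outcome can lie anywhere from 0/50 = 0% (all 45 late) to 45/50 = 90.0% (none late). The two Section 8 figures stay at 90.0% and 93.8% throughout.

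**Step 6. Check that the timed measure can be derived.** The recorded time points are one hour apart to Hour 6, then 6, 12, 12, 12 and 24 hours apart. A patient below 0.40 at Hour 2 whose first reduction is at Hour 3 meets the Section 5.1 window; one whose first reduction is at Hour 48 does not. The planned schedule separates them. The Section 8 wording does not.

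**The case against.** The best reply is that the sections complement each other. Section 5.1 defines outcomes, and Section 8 lists them in shorthand while adding operating detail. There is support for this. Section 5.1 iv.b excludes patients who did not continue treatment for the full six hours, and neither Section 8 nor Table 3 repeats that. Section 5.1 refers to weaning according to protocol, and Adherence vi supplies the amounts. In the same way, Adherence v could supply the trigger that Section 5.1 leaves open, while Section 5.1 supplies the window.

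That reading is possible, and it limits how much weight the point can carry. It does not remove it. Nothing in Section 8 or Table 3 carries the window over, the neighbouring items do restate their time limits, and even the combined reading leaves N undefined.

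A reader might go further and infer that FiO2 alone is an inadequate trigger, especially since Group A children can enter on acidosis or distress, and planned Group B children start support "irrespective of clinical condition". The SAP does not support this. It states no other weaning criterion, the protocol is not at hand, and the quoted words describe starting support after planned extubation. FiO2 below 0.40 at entry is a defect only if the weaning rule requires more, and this document does not show that.

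A reader might also object that the uneven spacing makes the next time point a poor yardstick. That would be a criticism of the pre-specified Section 5.1 window, not of the mismatch described here.

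**Conclusion.** The point holds. As written, Section 8 v and Table 3 either count late weaning as adherent or omit patients who were due to wean and never started, so they do not report the outcome defined in Section 5.1 iv.c. This follows from the wording alone and needs no assumption about the clinical trigger.

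The direction is clear under the first reading: the reported figure can never be below the timed one. The size is unknown. The 60.0%, 90.0% and 93.8% figures rest on assumed counts and illustrate the mechanism only. It would be tempting to say that the reported figure must come out close to 100%, but the SAP does not support that. Under the first reading, patients with FiO2 below 0.40 who never start weaning, for example because they cross over or are intubated first, stay in the denominator and lower the figure.

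Severity is moderate. This is one of two descriptive weaning items within one of six feasibility endpoints. The SAP attaches no threshold to it, and the only numeric target among those endpoints is randomising at least 50% of eligible patients. No treatment comparison depends on it.

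**What to change.** Reconcile Section 5.1 iv.c, Section 8 Adherence v and the Table 3 row so that all three describe one measure:

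- N = patients on allocated treatment who met the trial's weaning trigger at a recorded time point.
- n = those among N whose first reduction in flow (HFNC) or pressure (CPAP) was recorded by the next recorded time point.

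State the trigger once and refer to it in all three places; what that trigger should be is a clinical matter on which this point takes no view.

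The cost is SAP wording and one table row. The measure uses time points already recorded. The change should be made before the outcome data are inspected, in line with the SAP's own stated purpose.
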